where TBW is in kg; H, height in cm; W, weight in kg; R, resistance in ohms at 50 KHz. This equation was developed for both boys and girls and therefore is not sex-specific. Although this equation was developed and validated in a population from Peru , it was validated again in a population of preschool-aged children in urban India . They found that the FFM values that this equation predicted was in good agreement with those derived from TBW measured by D2O dilution . This equation was chosen for the PresPA study due similar characteristics between urban Indian preschoolers and urban Bangladeshi preschoolers and due to the fact that no equations validated in Bangladeshi children exist to date.

To determine FM from TBW, the hydration constants developed by Fomon and colleagues will be used, as they remain the reference standards for preschoolers: 0.775 (boys, 3 years), 0.779 (girls, 3 years) . TBW will be divided by these factors to calculate FFM (kg). FM (kg) is then determined by calculating the difference between total body weight (kg) and FFM (kg).

To evaluate the body composition of the female primary caregivers (usually mothers) of the preschoolers, we will use an equation validated in Bangladeshi postpartum women against H2O dilution criterion method:

$$TBW = 4.297 + 0.190*W + 0.349*H^2/R_{50}$$

where TBW is in kg; H, height in cm; W, weight in kg; R50, resistance in ohms at 50kHz . FFM (kg) can then be determined by dividing TBW by 0.732, assuming that this population's FFM has a hydration factor of 0.732 . FM (kg) is then determined by calculating the difference between total body weight (kg) and FFM (kg).

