### **10.3. Other covariates**

Other covariates will include: preschooler sex, preschooler anthropometric measures (e.g., height-for-age z-score, BMI-for-age z-score, waist circumference, and body fat percentage), maternal anthropometric measures (e.g., BMI, waist circumference, and body fat percentage), maternal and paternal socio-economic factors (educational level and household assets), and household food security status. Descriptions and derivations of each of these variables can be found in Table 2 (continuous variables) and Table 3 (categorical variables) (Appendix).

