### **10.4. Statistical Analysis**

#### **10.4.1. Primary Analysis**

Statistical analyses will be performed using STATA (College Station, TX). Data from Forms 1, 2, 3, 4, and the Accelerometry and GPS Log will be double entered in real time independently by research personnel. Data forms will be de-identified, such that only a participant ID number will be used to identify participants. Any discrepancies between data enterers will be flagged and reconciled by the student investigator. Data reconciliation will be conducted by the student investigator and will consist of reviewing the original hardcopy of the document and/or discussing the measure with the research assistant who had originally recorded it. Data review will consist of creating histograms, boxplots, and normal quantile-quantile (Q-Q) plots of each continuous variable to identify outliers and potentially implausible data.

Each day, the student investigator will assess the hardcopies of the data collection forms for missing data. In the case that data that can be collected over the telephone is missing (e.g., socioeconomic information, age, home perception questionnaire measures, etc.), if the missing data is flagged within 60 days of the date of initial collection, study personnel will reach out to the participant and their caregiver via telephone call to collect the measure of interest. If the missing data is flagged outside of the 60-day window of re-collection, the participant will be automatically opted out of that particular measure. In the case that data that must be collected in person is missing (e.g., body composition measures, dimensions of the home environment, hemoglobin concentration, etc.), if the missing data is flagged within 21 days of the date of initial collection, study personnel will reach out to the participant and their caregiver to schedule another home visit to collect the measure of interest (e.g., if measures are missing from the initial home visit, they may be collected in person during the final visit). In the case that the participant or their caregiver has opted out of a particular measure (e.g., hemoglobin concentration), they will not be included in analyses that involve that measure of interest.

**Objective #1:** Describe physical activity levels of the sample of preschoolers in urban Dhaka.

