***Descriptive statistics:***

We will calculate the mean and standard deviation of the following continuous measures:

- Area of available floor space indoors;
- Population density of indoor space (number of people dwelling in the home/total available area of indoor floor space);
- Height of stairwell railings (of those that had a railings); and

- Height of stove (of those who had stoves)

We will estimate the median and interquartile range of the following discrete measures:

- Number of rooms within the homes;
- Number of people who live in the home

We will generate tabular descriptions (frequencies and percents) of the following measures:

- Homes that had open stairwells (no railings);
- Homes that had minor (<1m^2) unfinished construction (of those who had unfinished construction);
- Those who had major (>1m^2) unfinished construction (of those who had unfinished construction);
- Building materials that the activity-facilitating items in the home are made of (e.g., clay, plastic, metal, wood, cloth, other).

We will use a mixed linear model with a random child-specific intercept. This is due to the repeated measures collected over the 7-day period for each participant. The physical activity data will be analyzed in activity counts per 15 second epochs, however to create multiple observations, we will nest the data by averaging the epochs over each of the 7 days to create 7 separate observations in each of the participant's datasets. This method was chosen since it will appropriately model the means and standard errors as well as properly handle missing data. We will use this model to estimate the unadjusted and multivariable-adjusted associations between each of the exposure variables (specified above) and PA level (counts/15s). Covariates that will be included in multivariable models will be pre-determined using a hypothesized directed acyclic graph (DAG).

***Objective #3: Estimate the associations between haemoglobin concentration (Hb) and preschooler physical activity level.***

To address our third objective, summary statistics (including mean, standard deviation, median, range, interquartile range) will be generated for hemoglobin (as a continuous variable) to help identify outliers and biologically implausible data.

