
Body fat percentage (female caregiver)
	
%
	
Data required (Form 2: Q10, 11, 12, 13, 17, 18):
 
 
• Height (m; average of 2 closest height measures)
 
• Weight (kg; average of 2 closest weight measures)
 
• Resistance (ohms measured at 50 kHz; average of the 2 closest resistance measures)
 
 
1) Total body water (TBW; kg) will be calculated using the following equation:  <math>TBW = 4.297 + 0.190 * Weight + 0.349 * Height^2 / Resistance</math>
 
2) To determine fat free mass (FFM; kg), TBW will be divided by a hydration factor of 0.732.
 
3) Fat mass (FM; kg) will be calculated by subtracting FFM from total weight.
 
4) Body fat percentage will be calculated using the following formula: <math>Body\ fat\ \% = (FM / Weight) * 100\%</math>

Body fat percentage (child participant)
	
%
	
Data required (Form 2: Q1, 2, 3, 4, 7, 8):
 
 
• Height (m; average of 2 closest height measures, value will be adjusted by subtracting 0.7 cm if recumbent length was measured)
 
• Weight (kg; average of 2 closest weight measures)
 
• Resistance (ohms measured at 50 kHz; average of the 2 closest resistance measures)
 
 
1) Total body water (TBW; kg) will be calculated using the following equation:  <math>TBW = 0.76 + 0.18 * Height^2 / Resistance + 0.39 * Weight</math>
 
2) To determine fat free mass (FFM; kg), TBW will be divided by a hydration factor of 0.775 (males) or 0.779 (females).

		
3) Fat mass (FM; kg) will be calculated by subtracting FFM from total weight.
 
4) Body fat percentage will be calculated using the following formula: <math>\text{Body fat \%} = (\text{FM}/\text{Weight}) * 100\%</math>

Number of children living in the home	Any integer	
Data required:
 
 
Form 3: Question 3
 

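### Table 2 lists height in metres for body-water equations that section 9.3.3 defines in centimetres; followed as written, body fat % all but ignores the impedance measurement

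*Combined protocol and SAP*

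**What the plan says.** Section 9.3.3 gives one TBW equation for the child and one for the female caregiver, and defines the symbols of each. For the child: "where TBW is in kg; H, height in cm; W, weight in kg; R, resistance in ohms at 50 KHz". For the caregiver: "H, height in cm; W, weight in kg; R 50 , resistance in ohms at 50kHz".

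Table 2 in section 17 (Appendix) sets out the full route to body fat % for both: TBW, then fat-free mass, then fat mass, then the percentage. The coefficients are those of section 9.3.3, but the height input differs. The female caregiver body-fat row asks for "Height (m; average of 2 closest height measures"), and the child body-fat row for "Height (m; average of 2 closest height measures, value will be adjusted by subtracting 0.7 cm if recumbent length was measured"). Neither row converts to cm or rescales a coefficient. The same wording appears in the two BMI rows of Table 2; metres are the right unit for caregiver BMI in kg/m², and those rows are not at issue here.

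Section 10.3 names body fat % among the child's anthropometric covariates and again among the "maternal anthropometric measures (e.g., BMI, waist circumference, and body fat percentage"). It points to the Appendix for the definitions: "Descriptions and derivations of each of these variables can be found in Table 2 (continuous variables").

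**The concern.** The document gives two incompatible derivations of the same variable and does not say which governs. Section 10.3 names Table 2 as the source, and Table 2 is a complete recipe that can be programmed without opening section 9.3.3.

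The error is not a constant shift that a regression coefficient would absorb. The term that shrinks is the only one carrying resistance, so the variation that makes bioelectrical impedance informative is lost. What remains is a transformation of body weight, with a small sex difference in children from the two hydration factors.

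What is at stake is limited to the adjusted models for objectives 2 and 3. Under objective 2 the plan says: "Covariates that will be included in multivariable models will be pre-determined using a hypothesized directed acyclic graph (DAG"), and objective 3 follows the same approach. If the graph selects child or maternal body fat %, the model would adjust for a recoded weight under the label of body fat. Mean counts per 15 seconds and the unadjusted associations do not depend on it.

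**Working it through.** The plan states no TBW or body fat result, so there is no figure of its own to reproduce. The check is to run its equations once in each unit.

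**Inputs from the documents** (section 9.3.3 and Table 2)
- Child: TBW = 0.76 + 0.18·H²/R + 0.39·W; hydration factor 0.775 (boys) or 0.779 (girls).
- Caregiver: TBW = 4.297 + 0.190·W + 0.349·H²/R; hydration factor 0.732.
- Fat-free mass = TBW / hydration factor; body fat % = 100·(W − fat-free mass)/W.

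**Assumed inputs.** The documents give no heights, weights or resistances. The values below are illustrations.

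**Step 1: the factor.** Height in m is height in cm divided by 100, so H² falls by 100² = 10,000. This needs no assumption.

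**Step 2: worked cases.**

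*Caregiver, 50 kg, 150 cm, 600 ohm*
- cm: impedance term 0.349 × 150²/600 = 13.09 kg; TBW = 4.297 + 9.50 + 13.09 = 26.88 kg; fat-free mass 26.88/0.732 = 36.73 kg; body fat (50 − 36.73)/50 = **26.5%**.
- m: impedance term 0.349 × 1.50²/600 = 0.0013 kg; TBW 13.80 kg; fat-free mass 18.85 kg; body fat **62.3%**.

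*Boy, 12.5 kg, 92 cm, 800 ohm*
- cm: impedance term 0.18 × 92²/800 = 1.90 kg; TBW = 0.76 + 1.90 + 4.875 = 7.54 kg; fat-free mass 7.54/0.775 = 9.73 kg; body fat **22.2%**.
- m: impedance term 0.00019 kg; TBW 5.64 kg; fat-free mass 7.27 kg; body fat **41.8%**.

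*Girl, same inputs, factor 0.779:* 22.6% with cm, 42.1% with m.

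With cm, the impedance term is 49% of the caregiver's TBW (13.09/26.88) and 25% of the boy's (1.90/7.54).

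**Step 3: what is left in metres.** Dropping the vanishing term:
- Caregiver: 100·(1 − 0.190/0.732) − 100·(4.297/0.732)/W = 74.04 − 587.0/W. At 50 kg this is 62.3%.
- Boy: 100·(1 − 0.39/0.775) − 100·(0.76/0.775)/W = 49.68 − 98.06/W. At 12.5 kg this is 41.8%.

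Neither height nor resistance appears.

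**Step 4: response to resistance alone.**

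| Case | Resistance | Change with cm | Change with m |
|---|---|---|---|
| Caregiver, 50 kg, 150 cm | 500 to 700 ohm | 12.3 points (19.4 to 31.7%) | 0.001 point |
| Boy, 12.5 kg, 92 cm | 700 to 900 ohm | 5.0 points (19.4 to 24.4%) | 0.0005 point |

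**Step 5: ranges over assumed grids.**

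| Group | Grid | cm | m | Ratio m/cm |
|---|---|---|---|---|
| Caregiver | 45–60 kg, 145–155 cm, 500–700 ohm | 10–40% | 61–64% | 1.6 to 6.0, median 2.2 |
| Child, both sexes | 11–14 kg, 88–96 cm, 700–900 ohm | 13–29% | 41–43% | 1.5 to 3.1, median 1.9 |

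The largest ratios come from the corners of the grids; the medians are more representative.

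**The case against.** The strongest reply is that this is a carried-over label with little reach. Section 9.3.3 introduces the equations, defines every symbol and gives the workable unit. The metre label in Table 2 sits in a list of required data and matches the BMI rows word for word. Body fat % is neither the outcome nor a listed exposure; it enters a model only if the causal graph selects it, and the named strata use BMI categories. The planned data review, with its "plots of each continuous variable to identify outliers and potentially implausible data", could expose caregivers clustered in the low sixties per cent. Nothing shows that metres were ever used in a calculation, and the values can be recalculated from recorded data.

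Most of this stands, and it limits the consequence. It does not remove the conflict. The table that section 10.3 designates for derivations gives the wrong input, and no text says section 9.3.3 overrides it. The data review is not a reliable safeguard either: in metres all values move together into a narrow band, so no single outlier need appear. The plan gives no plausibility range for body fat and does not say that derived variables are reviewed. One point of wording should be kept exact: section 10.3 lists no weight covariate, so the spoiled variable would not duplicate an existing weight term. It would be a near-deterministic function of weight, and of sex in children.

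**Conclusion.** The concern holds. As written, both body-fat rows of Table 2 contradict section 9.3.3, and following them reduces the impedance term by exactly 10,000. That factor, and the near-disappearance of resistance from the result, hold for any realistic data. The size of the shift rests on assumed inputs: about 36 percentage points for the caregiver case (62.3 − 26.5) and about 20 for the boy (41.8 − 22.2), with median ratios of 2.2 and 1.9 over the assumed grids. The effect is confined to adjusted models that include body fat %. This is a defect in the written derivation, not evidence that any value has been miscalculated. It should be corrected, but it does not touch the primary descriptive estimate.

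**What to change.** In the female caregiver and child body-fat rows of Table 2, give height in cm, in agreement with section 9.3.3. In the child row, apply the 0.7 cm recumbent-length subtraction in that same unit. Leave caregiver BMI in metres. Then confirm that the analysis code passes height in cm to both equations by comparing its output with one hand-worked case for each; the caregiver and boy cases above would serve.

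The cost is a unit change in two table rows and a short code check. If any values were computed in metres, they can be recalculated from the recorded height, weight and resistance.
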